6.3.5 Missing Data

For immunogenicity data, it may be reasonable to consider missing immunogenicity values as missing completely at random (MCAR), i.e., not informative. Therefore, each of the co-primary immunogenicity analyses will comprise a complete case analysis only, without introducing any bias. Imputation methods will not be used.

6.3.6 Interim Analysis

Not applicable.

6.3.7 Protocol Deviations

6.3.7.1 Definition of Protocol Deviation

Deviations from the protocol will be assessed as 'minor' or 'major'. CSR reportable ("major") protocol deviations (PDs) are defined in accordance with ICH E3 as important PDs related to study inclusion or

Statistical Analysis Plan

exclusion criteria, conduct of the trial, subject management or subject assessment resulting in the potential to jeopardize the safety or rights of the trial subjects or the scientific value of the trial.

All major PDs will be classified into the following categories, but not all deviations listed below will necessarily be declared a major PD:

- Informed Consent
- Inclusion/Exclusion criteria
- Withdrawal Criteria
- Investigational Product (IP) Admin/Study Treat
- Disallowed Medications
- Adverse Event (AE)/ Serious Adverse Event (SAE)
- Visit Schedule
- Procedure/Tests

Major PDs may result in exclusions of subject from one or more analysis sets according to study-specific PD codes specifications. Major protocol deviations that may lead to exclusion of the subject from the PPS are defined in Section 6.2.5.

The following PD summaries will be provided:

 Number and percentage of subjects with a major protocol deviation by type of deviation and vaccine group

A by-patient listing of protocol deviations will be provided.

6.3.7.2 Determination of Protocol Deviations

Prior to unblinding, a PD report will be provided to the Clinical Study Team (CST) consisting of medical, clinical, and operational team members from the Sponsor and CRO for review on an ongoing basis during the study. The PDs review is part of the Data Listing Review process.

After the review, the CST team is responsible for assessing the impact of PDs on the immunogenicity and safety data for study subjects from medical and clinical perspectives. The PDs will be identified and categorized to determine subjects to be excluded from analysis populations according to the PDs specification.

Details of PD review procedure will be provided in the Medical Monitoring Plan and Data Listing Review Manual.

PAREXEL International Statistical Analysis Plan

6.3.7.3 Exclusions of Individual Values for Safety Analysis

Some local and systemic adverse events (AEs) will be directly measured by the subject and will not be subject to a reconciliation process, even if they are biologically implausible. Therefore these implausible measurements will be removed from the analysis but included in listings. Implausible measurements are summarized in the Table 2 below:

Table 2: Implausible Solicited Adverse Events

Parameter	Implausible measurements
Body temperature	\leq 33°C or \geq 42°C
Erythema	Measurements ≥ 900 mm or Measurements < 0 mm
Induration	Measurements ≥ 500 mm or Measurements < 0 mm

6.3.8 Subject Disposition

The following subject data will be presented by treatment group and overall:

- The number of subjects screened
- The number of screen failures with a breakdown of reasons for screen failure
- The number of subject randomized
- The number of subjects dosed
- The number and percentage of subjects who completed treatment
- The number and percentage of subjects who discontinued from treatment with a breakdown of primary reasons for discontinuation from treatment
- The number and percentage of subjects who completed study
- The number and percentage of subjects who withdrew early from study with a breakdown of primary reasons for the early withdrawal.

Percentages of subjects will be based on the number of subjects randomized as 100%. All enrolled set will be used for subject disposition.

In addition, by-subject listings will be provided for subjects who discontinued the study early with reason for discontinuation.

PAREXEL International Statistical Analysis Plan

6.3.9 Demographic Data

All demographic data will be presented for the ITT, FAS, PPS, Safety Set and SSA1. All demographic and baseline characteristics will be listed and summarized overall and by treatment group using appropriate descriptive statistics. Continuous data will be summarized using the number of observations, mean, standard deviation, median, minimum and maximum. Categorical data will be summarized using frequency counts and percentages. No statistical hypothesis testing will be conducted.

6.3.10 Medical History

The frequencies and percentages of subjects with medical history will be presented by MedDRA system organ class and preferred term, by treatment group and overall. Medical history data will be tabulated for the ITT, FAS, PPS, and Safety Set.

6.3.11 Concomitant Medication

Concomitant medication will be summarized and listed for Safety Set. The frequencies and percentages of subjects reporting concomitant medications will be tabulated overall and by treatment group. Medications (generic drug name) will be coded using the WHO Drug dictionary.

Prior and concomitant procedures/non-drug therapies will be presented in a listing.

6.3.12 Exposure to the Investigational Medicinal Product

The number of subjects actually receiving the first, second and the third vaccination will be summarized by treatment group for safety population.

Vaccine administration information will also be listed.

6.3.13 Immunogenicity

The co-primary analyses of the immunogenicity data will be based on the PPS and FAS. Sensitivity analyses using the same approach will be conducted using the ITT. These analyses will be reported both with and without patients in the FAS or ITT who are seropositive at baseline.

Immunogenicity (measurement of anti-HBs titer) data will be listed by subject including actual sampling times relative to dosing. Serum concentrations will be summarized by treatment group. The following descriptive statistics will be presented for serum concentrations obtained at each nominal time point: n, geometric mean, geometric SD, median, minimum and maximum values.

Individual serum concentration versus actual times will be plotted by treatment group for anti-HBs antibody in linear and semi-logarithmic scale. The geometric mean serum concentrations with

Statistical Analysis Plan

corresponding 95% confidence intervals versus nominal times will also be presented. The bar plot of SPR by treatment on Days 28, 56 and 196 will also be produced based on PPS for all age groups and for age >= 45 years old. All treatment groups will be overlaid on the same plot.

6.3.13.1 Co-Primary Hypotheses

The two co-primary analyses will be tested in sequence, the test for superiority in the subgroup (≥ 45 years old) can only be conducted after non-inferiority in the overall population (≥ 18 years old) has already been shown.

1. Non-Inferiority of Sci-B-VacTM compared to Engerix-B® will be assessed using the PPS for the entire study population (i.e., adults ≥ 18 years old). The non-inferiority margin is set at 5%. The null and alternative hypotheses are as follows:

Null Hypothesis: SPR(Sci-B-VacTM) –SPR(Engerix-B®) <= -5%

Alternative Hypothesis: $SPR(Sci-B-Vac^{TM}) - SPR(Engerix-B@) > -5\%$

Non-inferiority will be assessed using the lower bound of the two-sided 95% confidence interval. If the lower bound is greater than -5%, Sci-B-VacTM will be declared non-inferior to Engerix-B®, and the study will be considered a success.

2. Superiority of Sci-B-Vac[™] compared to Engerix-B® will be assessed using the FAS for the study population of adults ≥ 45 years old who are sero-negative at baseline. In older adults, a 5% margin of superiority represents a clinically meaningful improvement at both the individual level and from a public health perspective, given the reduced immunogenicity of Engerix-B® in this population. Therefore a superiority margin is set at 5%. The null and alternative hypotheses are as follows:

Null Hypothesis: SPR(Sci-B-VacTM) – SPR(Engerix-B®) <= 5%

Alternative Hypothesis: $SPR(Sci-B-Vac^{TM}) - SPR(Engerix-B\mathbb{R}) > 5\%$

Superiority will be assessed using the lower bound of the two-sided 95% confidence interval. If the lower bound is greater than 0%, Sci-B-VacTM will be declared statistically superior to Engerix-B®. If the lower bound is greater than 5%, Sci-B-VacTM will be declared clinically superior to Engerix-B®, and the study will be considered a success.

6.3.13.2 Statistical Methods for Co-Primary Immunogenicity Analyses

Seroprotection rate (SPR) 4 weeks after the third injection

For the primary endpoint of SPR at day 196, 4 weeks following the third vaccination, data from all centers will be pooled for the primary analysis. The estimated difference in proportions [SPR(Sci-B-VacTM) –

Statistical Analysis Plan

SPR(Engerix-B®)] and two-sided 95% CIs, will be calculated using the Miettinen and Nurminen method. Funnel plot will be produced to investigate the impact of center.

Sample SAS code for assessment of non-inferiority:

• Sample SAS code for the analysis of binary data:

```
PROC FREQ; * specify and sub-select data set as applicable;
TABLES trt*seroprotection/riskdiff (cl=mn); * numerical 0/1-scores identify 'event';
RUN;
```

where seroprotection represent the seropositive event and trt represents treatment group.

If the lower bound of the 95% Miettinen-Nurminen CI is greater than -5%, Sci-B-Vac™ will be declared non-inferior to Engerix-B®.

Upon demonstrating non-inferiority in the overall population (≥ 18 years old), the test for superiority in the subgroup (≥ 45 years old) can be conducted. If the lower bound is greater than 0%, Sci-B-VacTM will be declared statistically superior to Engerix-B®. If the lower bound is greater than 5%, Sci-B-VacTM will be declared clinically superior to Engerix-B®.

Sensitivity analyses using the same approach outlined above will be conducted using the FAS for the non-inferiority co-primary analysis. These analyses will be reported both with and without patients in the FAS who are seropositive at baseline. Sensitivity analyses using the ITT analysis set will be conducted for the superiority co-primary analysis. For these ITT analyses, patients with missing data at Day 196 (4 weeks following the third vaccination) will be included and treated as failures. These analyses will be reported both with and without patients who are seropositive at baseline. Additional sensitivity analyses will be conducted using a Logistic Regression model, to adjust for age group. Factors for treatment and age group will be included in the model.

• Sample SAS code for the analysis of binary data using logistic regression:

```
PROC LOGISTIC; * specify and sub-select data set as applicable;
CLASS trt agegrp;
MODEL seroprotection = trt + agegrp * numerical 0/1-scores identify 'event';
LSMEANS trt /diff;
ODS OUTPUT lsmeans=lsmeans diffs=diffs;
RUN;
```

where seroprotection represent the seropositive event, trt represents treatment group and agegrp represents age group (18 - 44 years, 45 - 64 years, >=65 years).

The estimated proportion of responders (i.e., estimated responder rate) and the difference in the proportion of responders between Sci-B-VacTM and Engerix-B® will be estimated, as well as the 2-sided 95% CIs for the difference. The creation of the estimates of the proportions and difference in proportions will be completed using the process detailed below:

Statistical Analysis Plan

- 1. Use the logistic regression model to calculate:
 - a) Least squares mean estimates of the log odds of Sci-B-VacTM (Gc) and Engerix-B® (Gp), as well as their corresponding standard errors (S_C and S_P, respectively)
 - b) Standard error of the least squares mean estimate of the log odds ratio (S_R)
- 2. Compute estimates for predicted proportions using the following transformations:

$$P_C = \exp(G_C)/(1 + \exp(G_C))$$
$$P_P = \exp(G_P)/(1 + \exp(G_P))$$

The difference in proportions is then given by:

$$D = P_C - P_P$$

3. Estimate the standard error of D by:

$$S_D = sqrt[P_C^2 (1-P_C)^2 S_C^2 + P_P^2 (1-P_P)^2 S_P^2 + P_C (1-P_C) P_P (1-P_P) S_R^2 - P_C (1-P_C) P_P (1-P_P) (S_C^2 + S_P^2)]$$

Analyses of the co-primary endpoints will also be conducted and reported by key sub-groups using the sub-groups identified in Section 6.2.7.

• Sample SAS code for the subgroup analysis of binary data:

```
PROC FREQ; * specify and sub-select data set as applicable;

TABLES subgroup*trt*seroprotection/riskdiff (cl=mn); * numerical 0/1-scores identify 'event';
RUN;
```

where seroprotection represent the seropositive event, trt represents treatment group and subgroup represents subgroup defined in Section 6.2.7.

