1.2 Immunogenicity of licensed vaccines

Monovalent HBV vaccines, such as Engerix-B®, licensed in Canada, European Union (E.U), and the United States (U.S.) are second-generation vaccines using recombinant DNA technology to express the HBV DNA sequence coding for the small hepatitis B surface antigen (HBsAg) in yeasts. The 1 mL dose of Engerix-B® containing 20 µg of HBsAg is the form approved for the immunization of healthy adults. In adults, the most commonly recommended immunization schedule consists of three injections of vaccine: two injections 4 weeks apart, followed by a third injection 24 weeks after the initial injection.

A serum concentration of hepatitis B surface antigen antibody (anti-HBs) \geq 10 mIU/mL after vaccination is considered protective⁴, and is associated with long term immunity to hepatitis B⁵. Therefore, the seroprotection rate (SPR), i.e., the percentage of subjects achieving a serum concentration of hepatitis B surface antigen antibody (anti-HBs) \geq 10 mIU/mL after vaccination, is widely used as a surrogate endpoint for evaluating anti HBV vaccines.

While the SPRs elicited by currently licensed hepatitis B vaccines in children and adolescents are high (≥98%)⁶, up to 10% of all adults fail to achieve anti-HBs levels ≥10 mIU/mL after a three-dose schedule⁶, and are considered non-responders to hepatitis B vaccination. The proportion of adult non-responders is even higher in individuals age 30 years and above, where there is a well-documented age-dependent decline in response rate to currently licensed HBV vaccines^{7,8}. In recent phase 3 trials where Engerix-B® was the comparator, SPRs 4 weeks after completion of the three-dose regimen were 74%, 72% and 68%, in adults 40-49, 50-59 and 60-69 years old, respectively⁸⁻¹⁰. In addition to age and genetic factors, other factors are known are known to be associated with reduced immunogenicity of HBV, including obesity¹¹, and, as recently reviewed by Yang Tian et al in 2016, male gender, smoking, diabetes, and concomitant disease¹².

Moreover, compliance with the primary three-dose schedule is low, with up to 40% of vaccinees missing the third injection, resulting in inadequate clinical protection against HBV infection¹³.

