9.1 Sample size

The overall sample size for the study is driven by the superiority co-primary analysis in study subjects ≥ 45 years old. Assuming an SPR of 0.81 for Engerix-B® and 0.96 for Sci-B-Vac[™], a minimum of 540 subjects (270 per treatment group) provides 90% power to demonstrate superiority of SPR, assuming a 5% margin with a two-sided type 1 error of 0.05, i.e., to rule out a <5% difference in SPR based on the lower limit of the two-sided 95% confidence interval. Based on a targeted enrollment of 80% of study subjects age ≥45 years-old, an additional 180 (20%) 18-44 year old study subjects would be required, for a total of at least 680 subjects in the full study. A sample size of 680 would provide ≥ 90% power to demonstrate non-inferiority with a 5% margin if the Sci-B-Vac[™] SPR is as low as 0.88, with the same SPR for Engerix-B® (0.81), and the two-sided alpha is 0.05. A 5% margin of non-inferiority is justified by the > 90% SPR of Engerix-B® in young adults. In older adults, a 5% margin of superiority represents a clinically meaningful improvement at both the individual level and from a public health perspective, given the reduced immunogenicity of Engerix-B® in this population.

Given the desire to have robust immunogenicity estimates of SPR in the adult population following a three-dose regimen of Sci-B-Vac[™] and to guard against a better than expected SPR for Engerix-B[®] (up to 84% in subjects ≥45 years old), a total of 1,564 subjects will be enrolled to the trial. There will be targeted enrollment, with 80% (~n=1252) of the study population being ≥ 45 years old and 20% (~n=312) being 18-44 years old. This sample size will provide >90% power to establish the superiority of Sci-B-Vac[™] over Engerix-B[®] in older adults (≥45 years old) and non-inferiority in adults ≥ 18 years old, given the above statistical parameters.

Given the desire to have good representation across the spectrum of older adults, the targeted enrollment of adults \geq 45 years old (80%) will be divided equally between the 45-64 year old and \geq 65 year old strata.

Targeted enrollment by age strata will be as follows:

Age 18-44 years (20%): 312 (~ 156 per arm) Age 45-64 years (40%): 626 (~313 per arm) Age ≥ 65 years (40%): 626 (~313 per arm)

Enrollment within each stratum will be stopped once the target has been met.

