Sensitivity analyses using the same approach outlined above will be conducted using the FAS for both secondary analyses. These analyses will be reported both with and without patients in the FAS who are seropositive at baseline. Additional sensitivity analyses will be conducted using a Logistic Regression model, to adjust for age group. Factors for treatment and age group will be included in the model.

Analyses of the above secondary endpoints will also be conducted and reported by key sub-groups using the sub-groups identified in Section 6.2.7.

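### The age-adjusted logistic sensitivity analysis in adults 18 and over does not estimate the SPR difference it is labelled as: it weights the age groups equally and averages on the log-odds scale

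*SAP*

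**What the plan says.** SAP 6.1.1 defines SPR as the plain percentage of subjects who are seroprotected, and SAP 6.3.13.1 sets the -5% margin on the difference in SPR among all adults 18 and over. The decision rule in SAP 6.3.13.2 uses the unadjusted interval: "If the lower bound of the 95% Miettinen-Nurminen CI is greater than -5"%, non-inferiority is declared.

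The same section adds a logistic sensitivity analysis with treatment and three age groups (18-44, 45-64, 65 and over). The sample code requests "LSMEANS trt /diff" with no observed-margins option. The text then sets out three steps:

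- Step 1 obtains "Least squares mean estimates of the log odds of" each vaccine.
- Step 2 reads "Compute estimates for predicted proportions using the following transformations", namely exp(G)/(1+exp(G)).
- Step 3 gives a standard error for D, the difference of the two transformed values.

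The output is announced as follows: "The estimated proportion of responders (i.e., estimated responder rate) and the difference in the proportion of responders between" the vaccines. No age weights are stated.

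Protocol 9.1 sets unequal age targets: "Age 18-44 years (20%): 312", with 626 in each of the two older strata. SAP 6.3.13.3 ("Additional sensitivity analyses will be conducted using a Logistic Regression" model) and SAP 6.3.13.4 reuse the model without saying how proportions are derived from it.

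**The concern.** Two features of the recipe separate D from the SPR difference.

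1. Default least squares means average over the levels of age group with equal weight, so the 18-44 group counts for 33% instead of 20%.
2. The averaging is done on the log-odds scale before back-transformation. The inverse logit is not linear, so even with the right weights the result is not the average response probability.

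Both matter only if SPR varies with age, and the protocol says it does: section 1.2 describes a "well-documented age-dependent decline in response rate to currently licensed HBV vaccines".

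What is at stake is the value of the robustness check. If D differs from the primary estimate, a reader will put that down to age adjustment when part of it is an artefact of the computation. If D sits close to -5%, it may look reassuring when it should not. The per-arm responder rates reported beside it are not the arms' SPRs either.

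**Working it through.** **Inputs.** The age split reproduces: 312/1564 = 19.9% and 626/1564 = 40.0% twice, or 156/313/313 per arm. The planning SPRs for age 45 and over are 81% and 96% (SAP 4), and Engerix-B is put above 90% in young adults. The documents give no separate rates for 45-64 and 65 and over, so the age-specific rates are assumptions. The near-plan set is Engerix-B 92/85/77% and Sci-B-Vac 99/97/95%, whose older strata average 81% and 96%.

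**Method.** I fitted the SAP's model (treatment plus age group) to the expected counts and compared the SAP's D with the difference standardised to the enrolled age mix.

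**Near plan.** Fitted log odds are 2.496/1.729/1.201 for Engerix-B and 4.266/3.499/2.971 for Sci-B-Vac.

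- SAP recipe: the equal-weight means are 1.8088 and 3.5787. The inverse logits are 85.92% and 97.28%, so D = 11.36 points.
- Observed-margin weights: the means are 1.6709 and 3.4407, giving 84.17% and 96.90%, a difference of 12.73.
- Standardised: the fitted probabilities are 92.38/84.93/76.87% and 98.62/97.07/95.13%. For Engerix-B, (156 x 0.9238 + 313 x 0.8493 + 313 x 0.7687)/782 = 83.19%. The same sum for Sci-B-Vac is 96.60%. The difference is 13.40, equal to the crude SPR difference.

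Of the gap of 13.40 - 11.36 = 2.04 points, 12.73 - 11.36 = 1.37 is weighting and 13.40 - 12.73 = 0.67 is back-transformation. The lower limits are +8.6 (SAP) and +10.5 (standardised).

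**Steeper gradient** (92/80/65 vs 99/95/85%, below the planned rates in the older strata). The SAP gives 94.44 - 82.20 = 12.24, and standardisation gives 15.41. The Engerix-B rate is 82.2% against a true 76.4%.

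**At a true difference of -5.0 points.** Standardisation returned -5.00 in every case. The last three columns give the share of 10,000 simulated trials whose lower 95% limit exceeded -5% (Monte Carlo SE about 0.17 points).

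| Engerix-B rates (%) | Deficit | D | SAP | Standardised | Miettinen-Nurminen |
|---|---|---|---|---|---|
| 92/85/77 | uniform | -4.61 | 4.1% | 2.4% | 2.2% |
| 92/85/77 | 45 and over only | -4.42 | 5.5% | 2.5% | 2.3% |
| 92/85/77 | 65 and over only | -4.43 | 4.9% | 2.3% | 2.0% |
| 92/85/77 | -10/-3.75/-3.75 | -4.75 | 3.8% | 2.8% | 2.6% |
| 92/85/77 | 18-44 only | -5.04 | 2.6% | 2.6% | 2.5% |
| 92/80/65 | uniform | -4.62 | 4.1% | 2.6% | 2.3% |
| 92/80/65 | 65 and over only | -4.53 | 4.6% | 2.3% | 1.9% |
| 81 in all strata | uniform | -5.00 | 2.7% | 2.7% | 2.7% |

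**A single case where the reading flips.** With Engerix-B at 95/85/70% and a common odds ratio of 0.88, the lower limit is -4.75% by the SAP recipe, -5.7% standardised and -5.9% crude.

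**Age 45 and over.** The two strata are equal in size, so only the back-transformation error remains: 14.8 vs 15.0 near plan, and 4.96 or 5.05 at a true 5.0.

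**Standard error.** The SAP's formula is a correct delta-method expression for its own D. The fault lies in what D estimates.

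**The case against.** The strongest reply is that no decision depends on D. Success rests on the Miettinen-Nurminen bound, and the SAP attaches no threshold to the logistic result. That stands, and it limits the severity. In 5,000 simulated trials per setting at a true -5 (92/85/77, uniform deficit), the logistic interval cleared -5% in 4.0%, the primary in 2.3% and both in 2.3%. Every excess pass therefore occurred where the primary had already failed, so the percentages above are not false-claim rates for the trial. Even so, a failed primary is where a favourable sensitivity analysis is most likely to be cited.

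Second, the lenient direction needs Sci-B-Vac to be worse, which is far from the plan. Near plan the recipe is conservative and no conclusion changes. That also stands.

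Third, the equal weights are inferred from sample code, while the text is silent. This is true, but the logit-scale averaging and back-transformation are prescribed in the text, and observed-margin weights alone still leave 12.7 against 13.4.

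Fourth, an age-balanced contrast can be a legitimate estimand, and the planned differences by age group would help a reader diagnose a divergent D. The SAP, however, presents D as the difference in responder proportions, not as a separate estimand. The stratum results give no single age-adjusted overall estimate to set beside it.

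**Conclusion.** The concern holds. Followed as written, the SAP reports under the name of a responder proportion a quantity that is not the SPR. In adults 18 and over, D falls short of the SPR difference by about 2 points near plan and about 3 with a steeper age gradient, and the Engerix-B rate is overstated by about 3 to 6 points. At a true -5.0, D is shrunk toward zero by 0.25 to 0.6 points unless there is no age gradient or the deficit is confined to 18-44. All sizes rest on assumed age-specific rates and on the default equal weighting in the sample code; the direction follows from the age decline the protocol describes. The error is small in those aged 45 and over. The co-primary and secondary conclusions do not change, so this should be corrected but does not threaten the main result. For the secondary and exploratory analyses the problem arises only if the same steps are carried over.

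**What to change.** Replace the three steps in SAP 6.3.13.2 with standardised proportions. From the same logistic model, predict every analysed subject's probability under each vaccine, average over the analysed subjects, take the difference, and give a delta-method or bootstrap 95% interval. A risk difference stratified by age group with sample-size weights would also serve. Adding an observed-margins option to the existing code is not enough.

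State the same method in SAP 6.3.13.3 and 6.3.13.4 wherever the logistic model is used to report a difference in proportions. If equal age weights are intended, declare that as a separate estimand, label it so, and do not set it against the -5% margin.

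The cost is SAP wording and a few lines of code, with no new data and no change to the primary analysis.
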